# 6. STUDY OBJECTIVES AND ENDPOINTS

Core Primary Objective	Core Primary Endpoints
To evaluate the safety and tolerability of aducanumab over 100 weeks of treatment after a wash-out period imposed by discontinuation of feeder studies in participants who had previously received aducanumab (i.e., previously treated participants) or who had previously received placebo (i.e., treatment-naïve participants)	Incidence of AEs, SAEs, ARIA, and immunogenicity with over 100 weeks of treatment and/or re-exposure to aducanumab. Safety and tolerability parameters include the following:  Incidence of all AEs, AEs leading to treatment discontinuation or study withdrawal, and all SAEs  Incidence of ARIA-E and ARIA-H
	• Incidence of ADAs in serum

This clinical study collects samples that under separate optional consent may be used for future scientific and genetic research. Objectives related to this future research have not been determined.

#### 7. STUDY DESIGN

# 7.1. Study Overview

Study 221AD304 is an open-label, multicenter, longitudinal, single-arm, global Phase 3b study in participants with Alzheimer's disease who had participated in feeder studies. It is calculated that up to approximately 2400 participants (see Section 16.7) will be enrolled across approximately 350 sites globally. The primary study objective is to evaluate the long-term safety and tolerability of a monthly dose (10 mg/kg) of aducanumab after a gap period imposed by discontinuation of feeder studies.

After a Screening Period of approximately 8 weeks, participants who meet the eligibility criteria will receive open-label treatment. During the Core Treatment Period, participants will receive IV infusions of aducanumab approximately Q4W for a duration of 100 weeks (a total of 26 doses). The aducanumab dosing regimen will be 10 mg/kg following this titration: 1 mg/kg for the first 2 doses, 3 mg/kg for the next 2 doses, 6 mg/kg for the next 2 doses, and 10 mg/kg thereafter. Eligible participants will then enter the LTE treatment period and continue dosing on 10 mg/kg aducanumab Q4W for an additional 52 weeks (a total of 152 weeks of continuous treatment). The EOT Visit will occur at Week 154. Participants will have a safety FU Visit 18 weeks after their last dose of study treatment.

See Section 5.3.1 for details of dosing scheme.

Individual dose adjustments may also be implemented in participants who develop ARIA. See Section 7.2.1.

# 7.2. Study Specifics

#### 7.2.1. Dose Suspension or Discontinuation for ARIA Events

Discontinuation of Dosing for a Given Participant

The central MRI reading center will report incident events of ARIA-E and ARIA-H to both the Sponsor and the Investigator within a specified time after observing the finding on MRI per the imaging manual procedures. All events of ARIA will be reviewed by the Sponsor and the Investigator; decisions on dosing continuation, interruption, or discontinuation will be based on clinical symptoms, and the radiographic severity scoring on the MRI report provided by the central reader. The Investigator must review the MRI report prior to next dosing. Guidelines on the management and disposition of ARIA-E and ARIA-H events (including the criteria to be met for the continuation, suspension/resumption, permanent discontinuation of dosing due to ARIA, resumption of dosing after dose suspension due to ARIA [including rules for titrating up to the assigned dose], and management of recurrent ARIA) are provided in the following subsections. After each ARIA event, will be collected at the time of the first unscheduled visit following the event. Dosing may also be terminated at the discretion of the Sponsor for medical reasons. See Section 10.1 for the full list of criteria for discontinuing study treatment.

#### **7.2.1.1. ARIA-E Events**

**Table 8:** Disposition of ARIA-E Events

Clinical Symptom Severity	ARIA-E Severity on MRI (Central Read)		
	Mild	Moderate	Severe
Asymptomatic	Continue dosing at current dose and schedule	1 0	e ARIA-E resolves the dosing at the same dose.
Mild			
Moderate			
Severe	Suspend dosing. Once ARIA-E and clinical symptoms resolve, the participant may resume dosing at the same dose.		
Serious "other medically important event" only 			
Serious, except for "other medically important event" 	Discontinue dosing		

<sup>1 "Other medically important events" requiring dose suspension include SAEs that are not life-threatening (in the opinion of the Investigator), do not require inpatient hospitalization or prolongation of existing hospitalization, and do not result in significant/permanent disability or congenital anomalies/fetal defects, but may (in the opinion of the Investigator) jeopardize the participant or may require intervention to prevent one of the outcomes listed above and as described in Section 15.1.2.

- Participants who develop mild ARIA-E, per central MRI reading, with no clinical symptoms during the episode of ARIA-E, may continue in the study at their current dose. Participants should complete all scheduled clinic visits for assessments and, in addition, have an unscheduled visit for an MRI and until the ARIA-E has resolved per the centrally read MRI.
- Participants who develop **moderate or severe ARIA-E**, **per central MRI reading**, **with no clinical symptoms** during the episode of ARIA-E will temporarily suspend treatment, but should complete all scheduled clinic visits for assessments and, in addition, have an unscheduled visit for an MRI and until the ARIA-E has resolved per the centrally read MRI. If the ARIA-E resolves and the participant remains asymptomatic (in the Investigator's opinion), the participant may resume treatment at the same dose.
- Participants who develop mild, moderate, or severe ARIA-E, per central MRI reading, accompanied by clinical symptoms during the episode of ARIA-E will temporarily suspend treatment, but should complete all scheduled clinic visits for assessments and, in addition, have an unscheduled visit for an MRI and until the ARIA-E has resolved per the centrally read MRI. If the ARIA-E

<sup>2 SAEs requiring permanent discontinuation of study treatment include those that are life-threatening (in the opinion of the Investigator), require inpatient hospitalization or prolongation of existing hospitalization, and/or result in persistent or significant disability/incapacity or a congenital anomaly/birth defect as described in Section 15.1.2.

- resolves and the clinical symptoms resolve (in the Investigator's opinion), the participant may resume treatment at the same dose.
- Participants who develop mild, moderate, or severe ARIA-E, per central MRI reading, accompanied by serious (except "other medically important event") clinical symptoms related to the current episode of ARIA-E will permanently DCT but remain in the study. Participants should complete a safety FU Visit 18 weeks after the last dose of study treatment, protocol-required tests and assessments at a subset of the clinic visits (see Table 5), and, in addition, have an unscheduled visit for an MRI and until the ARIA-E has resolved per centrally read MRI.

See Section 7.2.1.6 for details on resumption of dosing when suspension occurs during the titration period and Section 7.2.1.7 for guidelines on resuming dosing after a recurrence of ARIA.

#### 7.2.1.2. ARIA-H (Micro-hemorrhage)

In this study, new incident micro-hemorrhages are defined as micro-hemorrhages that start after aducanumab infusion per this study (221AD304) and do not include micro-hemorrhages seen on the baseline MRI done for this study.

Table 9: Disposition of ARIA-H (Micro-hemorrhage) Events

Clinical	New Inc	l Read)		
Symptom	Mild	Moderate	Severe	
Severity	≥ 1 and ≤ 4	≥ 5 and ≤ 9	≥ 10	
Asymptomatic	Continue dosing at current dose and schedule	Suspend dosing. Once ARIA-H is stable, the participant may resume dosing at the same dose.		
Mild				
Moderate				
Severe	Suspend dosing. Once ARIA	-H stabilizes and clinical symptoms		
Serious "other medically important event" only 	resolve, the participant may resume dosing at the same dose.  Discontinue dosing		Discontinue dosing	
Serious, except for "other medically important event" 				

<sup>1 New incidence of micro-hemorrhages = new micro-hemorrhages that start after aducanumab infusion per this study (221AD304), does not include micro-hemorrhages seen on the baseline MRI done for this study.

#### Asymptomatic ARIA-H (Micro-hemorrhage)

• Participants who develop a ≥ 1 and ≤ 4 new incident micro-hemorrhage(s) [mild] at any time during the study may continue treatment at the current dose. Participants should complete all scheduled clinic visits for assessments and, in addition, have an unscheduled visit for an MRI and until the ARIA-H micro-hemorrhage is confirmed stable per the centrally read MRI. Micro-hemorrhages are considered stable if there is no change or a decrease in the number, size, severity, or number of locations between 2 consecutive MRIs including the initial detection MRI and the MRI performed 4 weeks (± 5 days) later.

<sup>2 "Other medically important events" requiring dose suspension include SAEs that are not life-threatening (in the opinion of the Investigator), do not require inpatient hospitalization or prolongation of existing hospitalization, and do not result in significant/permanent disability or congenital anomalies/fetal defects, but may (in the opinion of the Investigator) jeopardize the participant or may require intervention to prevent one of the outcomes listed above as described in Section 15.1.2.

<sup>3 SAEs requiring permanent discontinuation of study treatment include those that are life-threatening (in the opinion of the Investigator), require inpatient hospitalization or prolongation of existing hospitalization, and/or result in persistent or significant disability/incapacity or a congenital anomaly/birth defect as described in Section 15.1.2.

- Participants who develop ≥ 5 and ≤ 9 new incident micro-hemorrhages (moderate) at any time during the study will temporarily suspend treatment, but should complete all scheduled clinic visits for assessments and, in addition, have an unscheduled visit for an MRI and until the micro-hemorrhage is confirmed as stable per the centrally read MRI. Once the micro-hemorrhage is deemed stable, participants may resume treatment at the same dose.
- Participants who develop ≥ 10 new incident micro-hemorrhages (severe) at any time during the study will permanently DCT but remain in the study. Participants should complete a safety FU Visit 18 weeks after the last dose of study treatment, protocol-required tests and assessments at a subset of the clinic visits (see Table 5), and, in addition, have an unscheduled visit for an MRI and until the micro-hemorrhages are deemed stable per centrally read MRI.

## **Symptomatic ARIA-H (Micro-hemorrhage)**

- Participants who develop ≤ 9 new incident micro-hemorrhages (mild or moderate) and associated mild, moderate, severe, or serious ("other medically important event" only [Section 15.1.2]) clinical symptoms will temporarily suspend treatment, but should complete all scheduled clinic visits for assessments and, in addition, have an unscheduled visit for an MRI and until the ARIA-H micro-hemorrhage(s) is confirmed stable per the centrally read MRI. Once ARIA-H (micro-hemorrhage) is deemed stable and the clinical symptoms have resolved (in the Investigator's opinion), the participant may resume treatment at the same dose.
- Participants who experience serious (except "other medically important event" [Section 15.1.2]) clinical symptoms associated with micro-hemorrhage(s) (independent of the radiographic severity of the event) will permanently DCT but remain in the study. Participants should complete a safety FU Visit 18 weeks after the last dose of study treatment, protocol-required tests and assessments at a subset of the clinic visits (see Table 5), and, in addition, have an unscheduled visit for an MRI and until the micro-hemorrhage(s) is confirmed stable per centrally read MRI.
- Participants who develop ≥ 10 new incident micro-hemorrhages (severe), regardless of the presence of clinical symptoms, during the study, will permanently DCT but remain in the study. Participants should complete a safety FU Visit 18 weeks after the last dose of study treatment, protocol-required tests and assessments at a subset of the clinic visits (see Table 5), and, in addition, have an unscheduled visit for an MRI and until the micro-hemorrhages are deemed stable per centrally read MRI.

See Section 7.2.1.6 for details on resumption of dosing when suspension occurs during the titration period and Section 7.2.1.7 for guidelines on resuming dosing after a recurrence of ARIA.

#### 7.2.1.3. ARIA-H (Superficial Siderosis)

In this study, for participants previously treated with aducanumab, new incident focal areas of superficial siderosis are defined as new incident focal areas of superficial siderosis that occur on treatment and do not include focal areas of superficial siderosis seen on baseline MRI.

Table 10: Disposition of ARIA-H (Superficial Siderosis) Events

Clinical	New Inciden	entral Read)	
Symptom	Mild	Moderate	Severe
Severity	1	2	>2
Asymptomatic	Continue dosing at current dose and schedule	Suspend dosing. Once ARIA-H is stable the participant may resume dosing at the same dose.	
Mild	 		
Moderate			
Severe		spend dosing. Once ARIA-H stabilizes and clinical	
Serious "other medically important event" only 	symptoms resolve, the participant may resume dosing at the same dose.		Discontinue dosing
Serious, except for "other medically important event" 	Disco	ontinue dosing	

<sup>1 New incident superficial siderosis = new incident superficial siderosis on treatment.

#### **Asymptomatic ARIA-H (Superficial Siderosis)**

• Participants who develop a **single new incident focal area of hemosiderosis** (**also referred to as superficial siderosis**) [mild] at any time during the study may continue treatment at the current dose, but must have an unscheduled visit for an MRI and until the superficial siderosis is confirmed as stable per the centrally read MRI. Superficial siderosis is considered stable if there is no change or a decrease in the number, size, severity, or number of locations between 2 consecutive MRIs, including the initial detection MRI and the MRI performed 4 weeks (± 5 days) later.

<sup>2 "Other medically important events" requiring dose suspension include SAEs that are not life-threatening (in the opinion of the Investigator), do not require inpatient hospitalization or prolongation of existing hospitalization, and do not result in significant/permanent disability or congenital anomalies/fetal defects, but may (in the opinion of the Investigator) jeopardize the participant or may require intervention to prevent one of the outcomes listed above as described in Section 15.1.2.

<sup>3 SAEs requiring permanent discontinuation of study treatment include those that are life-threatening (in the opinion of the Investigator), require inpatient hospitalization or prolongation of existing hospitalization, and/or result in persistent or significant disability/incapacity or a congenital anomaly/birth defect as described in Section 15.1.2.

- Participants who develop 2 new focal areas of hemosiderosis (superficial siderosis) [moderate] occurring at any time during the study will temporarily suspend treatment, but should complete all scheduled clinic visits for assessments and, in addition, have an unscheduled visit for an MRI and until the ARIA-H (superficial siderosis) is confirmed as stable per the centrally read MRI. Once the superficial siderosis is deemed stable, the participants may resume treatment at the same dose.
- Participants who develop > 2 new focal areas of hemosiderosis (superficial siderosis) [severe] at any time during the study must permanently DCT but remain in the study. Participants should complete a safety FU Visit 18 weeks after the last dose of study treatment, protocol-required tests and assessments at a subset of the clinic visits (see Table 5), and, in addition, have an unscheduled visit for an MRI and until the ARIA-H (superficial siderosis) is confirmed as stable per the centrally read MRI.

## Symptomatic ARIA-H (Superficial Siderosis)

- Participants who develop ≤ 2 new focal areas of superficial siderosis (mild or moderate) associated with mild, moderate, severe, or serious ("other medically important event" only) clinical symptoms will temporarily suspend treatment, but should complete all scheduled clinic visits for assessments and, in addition, have an unscheduled visit for an MRI and until the ARIA-H superficial siderosis is confirmed stable per the centrally read MRI. Superficial siderosis is considered stable if there is no change or a decrease in the number, size, severity, or number of locations between 2 consecutive MRIs including the initial detection MRI and the MRI performed 4 weeks (± 5 days) later. Once the ARIA-H (superficial siderosis) is deemed stable and the clinical symptoms have resolved (in the Investigator's opinion), the participants may resume treatment at the same dose.
- Participants who experience serious (except "other medically important event" [Section 15.1.2]) clinical symptoms associated with ARIA-H (superficial siderosis) will permanently DCT but remain in the study. Participants should complete a safety FU Visit 18 weeks after the last dose of study treatment, protocol-required tests and assessments at a subset of the clinic visits (see Table 5), and, in addition, have an unscheduled visit for an MRI and until the superficial siderosis is confirmed stable per centrally read MRI.
- Participants who develop >2 new focal areas of superficial siderosis (severe), regardless of the presence of clinical symptoms, will permanently DCT but remain in the study. Participants should complete a safety FU Visit 18 weeks after the last dose of study treatment, protocol-required tests and assessments at a subset of the clinic visits (see Table 5), and, in addition, have an unscheduled visit for an MRI and until the superficial siderosis is confirmed stable per centrally read MRI.

See Section 7.2.1.6 for details on resumption of dosing when suspension occurs during the titration period and Section 7.2.1.7 for guidelines on resuming dosing after a recurrence of ARIA.

## 7.2.1.4. ARIA-H (Macro-hemorrhage)

Participants who develop any new incident of macro-hemorrhage (defined as > 1 cm in diameter on T2\* MRI sequence), regardless of the presence of clinical symptoms, will permanently DCT, but should remain in the study. Participants should complete a safety FU Visit 18 weeks after the last dose of study treatment, protocol-required tests and assessments at a subset of the clinic visits (see Table 5) and, in addition, have an unscheduled visit for MRI and or on a clinically indicated, until the macro-hemorrhage is confirmed stable per centrally read MRI. A macro-hemorrhage is considered stable if there is no change or a decrease in the number, size, severity, or number of locations between 2 consecutive MRIs, including the initial detection MRI and the MRI performed 4 weeks (± 5 days) later.

#### 7.2.1.5. Coincident ARIA-H and ARIA-E Events

Participants who develop ARIA-H coincident with ARIA-E at any time during the study will follow the most restrictive guidelines. Prior to resuming treatment, where applicable, ARIA-E must resolve, ARIA-H must be deemed stable, and the participant must be asymptomatic. For example, if a participant experiences radiographically mild ARIA-H (1 to 4 micro-hemorrhages) coincident with radiographically moderate ARIA-E, the participant will temporarily suspend treatment per the ARIA-E guidelines summarized in Table 8. In addition, unscheduled visits should occur as described in Section 7.2.1.1, Section 7.2.1.2, Section 7.2.1.3, and Section 7.2.1.4.

## 7.2.1.6. Resumption of Study Treatment After Suspension due to ARIA

#### **7.2.1.6.1. MRI Monitoring**

When treatment resumes after a dose suspension due to ARIA, an MRI and will be performed 2 weeks (± 5 days) after the second administration of the restarted dose. This visit will also include a physical and neurological examination and collection of vital signs.

In addition, if treatment was suspended during the dose titration prior to the participant reaching the 10 mg/kg dose, an MRI and will be performed 2 weeks (± 5 days) after every second dose until completion of the titration period with a final MRI after the second dose at 10 mg/kg, not counting unscheduled MRI visits for monitoring of ongoing ARIA, MRIs will otherwise be performed as indicated in the Schedule of Events (Section 4.2).

#### 7.2.1.6.2. Dosing Upon Resumption of Study Treatment

Participants who suspend treatment due to ARIA may resume treatment at the same dose if they meet the criteria as described in Section 7.2.1.1, Section 7.2.1.2, Section 7.2.1.3, Section 7.2.1.4, and Section 7.2.1.5. Participants who suspend and then resume dosing after having already reached 10 mg/kg are to continue dosing at that dose. However, if dosing is suspended prior to a participant reaching 10 mg/kg, the participant (1) must receive at least 2 doses at the restart dose

before titrating up to the next dose level and (2) must complete at least the required number of doses at that dose level per the titration schedule, as outlined in the right column of Table 11.

Table 11: Resumption of Study Treatment Following Dose Suspension Due to ARIA During Titration

Dose Level at Which ARIA Occurred	Number of Doses Prior to ARIA	Number of Doses at Current Dose Level Needed Before Going to the Next Higher Dose
1 mg/kg	1	2
1 mg/kg	2	2
3 mg/kg	1	2
3 mg/kg	2	2
6 mg/kg	1	2
6 mg/kg	2	2

## 7.2.1.7. Management After Recurrent ARIA (Dosing and MRI)

If the participant has more than one occurrence of ARIA (i.e., a second episode of ARIA-E or new incident ARIA-H micro-hemorrhages or superficial siderosis), after the ARIA resolves or stabilizes, the participant is to resume dosing at the same dose as that described in Section 7.2.1.6.2. Once dosing has resumed, the guidelines outlined in Table 11 apply if the participant is still in the titration period. If a participant resumes treatment after ARIA, an MRI and will be performed 2 weeks (± 5 days) after the second administration of the restarted dose, and 2 weeks (± 5 days) after every second dose until the completion of titration (if applicable). MRIs will otherwise be performed as indicated in the Schedule of Events (Section 4.2).

#### 7.2.2. Infusion Interruption

If any mild or moderate symptoms occur during a treatment infusion, the infusion should be slowed or interrupted, and supportive treatment should be instituted at the discretion of the Investigator. After resolution of symptoms, if the infusion had been slowed, the original infusion rate may be resumed; if the infusion had been interrupted, the infusion may be restarted at a rate that does not exceed the original infusion rate. An infusion must be discontinued if not completed within 3 hours.

Refer to the DHA for infusion rate information.

If a severe infusion-related reaction occurs during an infusion, or an allergic reaction such as urticaria or anaphylaxis occurs, the participant will be discontinued from study treatment but may remain in the study. The participant must be appropriately treated in accordance with local practice.

Severity of events is described in Section 15.2.3.

[figure not shown]

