# 10. DISCONTINUATION OF STUDY TREATMENT AND/OR WITHDRAWAL OF PARTICIPANTS FROM THE STUDY

## **10.1.** Discontinuation of Study Treatment

A participant *must* permanently discontinue study treatment for any of the following reasons:

- The participant develops any of the following:
  - ARIA-E accompanied by serious clinical symptoms except for "other medically important event" as defined in Table 8.
  - Symptomatic ARIA-H (micro-hemorrhages) with serious clinical symptoms except for "other medically important event" as defined in Table 9.
  - Symptomatic ARIA-H (superficial siderosis) with serious clinical symptoms except for "other medically important event" as defined in Table 10.
  - ARIA-H with ≥ 10 new incident micro-hemorrhages and/or > 2 new incident focal areas of superficial siderosis. (Note: Only new, treatment-emergent events occurring in the study are counted).
  - Any new incident macro-hemorrhage (defined as > 1 cm in diameter on T2\* sequence).

See Section 7.2.1 for full details regarding discontinuation due to ARIA-E or ARIA-H.

- The participant becomes pregnant. Study treatment must be discontinued immediately and pregnancy must be reported according to the instructions in Section 15.4.1.
- The participant withdraws consent to continue study treatment.
- The participant experiences a medical emergency that necessitates permanent discontinuation of study treatment.
- The participant experiences an AE that does not resolve or requires continued treatment that meets exclusionary criteria (see Section 11.5.1.2).
- The participant experiences a severe infusion reaction.
- At the discretion of the Investigator for medical reasons.
- At the discretion of the Investigator or Sponsor for noncompliance or other reasons.

The reason for discontinuation of study treatment must be recorded in the participant's CRF.

A participant who discontinues treatment is to remain in the study, attend a safety FU Visit 18 weeks after the last dose of study treatment, and immediately continue protocol-required tests and assessments at a subset of the clinic visits (see Table 5) until the end of the study per the Schedule of Events or until the participant withdraws consent.

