5.7.4. Other Significant AEs

CNS Hemorrhage, Seizures, falls, and hypersensitivity reactions are considered significant AEs and are being monitored in this study. As listed in Table 6, CNS hemorrhage, seizures, hypersensitivity, and fall events will be summarized by safety analysis groups and will be listed.

CNS hemorrhage events will be identified by the eCRF and by using a standardized MedDRA query (SMQ), consisting of selected preferred terms within SMQ of "Haemorrhagic central nervous system vascular conditions" (narrow and broad scope). The SMQ list of PTs may be modified based on newer version of MedDRA when available and safety team's discretion. All CNS hemorrhage events will be summarized by preferred term. A separate summary table will be presented with all hemorrhagic CNS vascular conditions except subdural hematomas.

Seizure events will be identified using the SMQ of "Convulsions" (narrow and broad scope). ARIA status of subjects with seizure will be presented, splitting by the number of subjects with non-evaluable ARIA status (no post-baseline MRI), subjects with no ARIA event during the study and subjects who experienced ARIA during the study.

Hypersensitivity events will be identified using the SMQ of hypersensitivity (narrow and broad scope), SMQ of angioedema (narrow and broad scope) and SMQ of anaphylactic reaction (narrow and broad scope). The SMQ list of PTs may change due to the newer version of MedDRA and at the safety team's discretion.

Fall events will be identified based on the preferred term "Fall" and number of falls will be presented.

Table 6 List of Planned Analyses for ARIA and Other Significant AEs

Analysis	Repeat stratified by ?	Repeat by Core Treatment Period?
Incidence of ARIA events by previous ARIA-E experience	Yes	Yes
Maximum MRI severity and worst symptomatic status of ARIA events	Yes	Yes
Maximum MRI severity and worst symptomatic status of ARIA events among participants with ARIA	No	Yes
Onset of ARIA events	No	Yes

Product: Aducanumab

Statistical Analysis Plan

Study: 221AD304 Version: 2.0

Analysis	Repeat stratified by ?	Repeat by Core Treatment Period?
Resolution of ARIA-E and stabilization of ARIA-H	No	Yes
Summary of first ARIA-E	No	Yes
Recurrent ARIA-E	No	Yes
ARIA-related adverse events by SOC/PT	No	Yes
Summary of symptomatic ARIA	No	Yes
Summary of serious and severe ARIA and symptoms	No	Yes
Serious or severe ARIA-related adverse events by PT	No	Yes
Summary of ARIA-H events by ARIA-E status	No	Yes

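### Protocol Sections 7.2.2 and 10.1 do not give the same instruction for a non-severe allergic reaction, which bears on participant safety and on the count of adverse events that lead to stopping treatment

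*Protocol*

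**What the plan says.** Four pieces of protocol text bear on an allergic reaction to an infusion.

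- Section 7.2.2, first paragraph: "If any mild or moderate symptoms occur during a treatment infusion, the infusion should be slowed or interrupted". After symptoms resolve, the original rate may be resumed or the infusion restarted. Allergic symptoms are not excepted.
- Section 7.2.2, later paragraph: "If a severe infusion-related reaction occurs during an infusion, or an allergic reaction such as urticaria or anaphylaxis occurs, the participant will be discontinued". The word severe qualifies the infusion-related limb only.
- Section 10.1, list of mandatory reasons for permanent discontinuation: "The participant experiences a severe infusion reaction". Allergic reaction, urticaria and anaphylaxis do not appear. The list also contains a discretionary entry: "At the discretion of the Investigator for medical reasons".
- Section 7.2.1, on the status of that list: "See Section 10.1 for the full list of criteria for discontinuing study treatment".

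The endpoint concerned is in Protocol Section 6, where the first safety parameter under the core primary endpoints reads: "Incidence of all AEs, AEs leading to treatment discontinuation or study withdrawal, and all SAEs". SAP Section 2.1.1 repeats it, and SAP Table 4 tabulates the events that led to discontinuation by system organ class and preferred term, for the whole study and for the core period.

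**The concern.** A stopping rule should give one answer for one event. Here, a site that meets a mild allergic reaction finds one paragraph that tells it to slow or pause and then go on, another that tells it to end treatment, and a list described as complete that does not mention the case. Which text the site acts on decides whether the participant is dosed again.

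Two things are at stake. The first is participant safety, because the rule governs further exposure after an allergic reaction. The second is the meaning of a primary endpoint component: the proportion whose adverse event ended treatment reflects partly what happened to participants and partly which paragraph their site applied. In a single-arm study there is no comparator in which the same inconsistency would cancel.

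**Working it through.** The plan gives no figure to reproduce: no sample size was determined (Protocol Section 16.7, SAP Section 2.4) and nothing is tested (SAP Section 5.1). The check is a comparison of texts on one test case.

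**Step 1, the test case.** Section 7.2.2 refers to Section 15.2.3 for severity. That section grades by discomfort and effect on functioning, not by diagnosis, so urticaria can be graded mild or moderate. Take mild urticaria during an infusion.

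**Step 2, what each provision says about it.**

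| Provision | Condition | Met? | Instruction |
|---|---|---|---|
| 7.2.2, first paragraph | Mild or moderate symptoms during infusion | Yes | Slow or interrupt; may resume after resolution |
| 7.2.2, later paragraph, infusion-reaction limb | Severe infusion-related reaction | No | None |
| 7.2.2, later paragraph, allergic limb | Allergic reaction, urticaria being a named example | Yes | End study treatment |
| 10.1, infusion-reaction entry | Severe infusion reaction | No | None |
| 10.1, discretionary entries | Judgement of the investigator or sponsor | Optional | Stopping allowed, not required |

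**Step 3, combining them.** The first paragraph of 7.2.2 with 10.1 leaves continuation open. The allergic limb of 7.2.2 requires "or an allergic reaction such as urticaria or anaphylaxis occurs, the participant will be discontinued from study treatment but may remain in the study". The same event satisfies both conditions in 7.2.2, and 10.1 does not settle the matter because it leaves the case out while being called complete.

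**Step 4, where the mismatch applies.** A severe reaction during an infusion is a stopping reason in both sections, and 10.1 also covers a medical emergency that makes stopping necessary. The disagreement is therefore about allergic reactions that are not severe.

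**Step 5, the route to the endpoint.** The urticaria is counted as an adverse event whichever paragraph is followed. What changes is whether it enters the SAP Table 4 row for events that led to discontinuation.

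**Step 6, scale.** The documents give no rate of non-severe allergic reactions and no information on which text sites followed, so the number affected cannot be derived. The effect per participant can be bounded. SAP Section 2.4 gives 1696 enrolled. The denominator is the safety population (at least one dose), whose size is not stated and which should not exceed 1696. One participant handled differently moves the overall proportion by at least 1/1696 = 0.00059, or 0.059 percentage points. Within a single prior-exposure group the movement is larger; the group sizes are not given.

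**The case against.** The strongest reply is that this is an omission, not a clash. Section 10.1 nowhere says that treatment goes on after a non-severe allergic reaction, and its discretionary entries allow stopping, so a site that stops satisfies every provision. Section 7.2.2 also has an ordinary reading: its first paragraph manages the infusion in progress, while its later sentence, being specific to allergic reactions, governs further treatment. In addition, Section 12 gives precedence to the Directions for Handling and Administration on how the product is administered. That document is not available here, so the infusion-handling instruction that sites held is unknown. Finally, SAP Sections 1 and 2.3 show that everyone had completed the core period by 19 September 2023 and that the last doses, in France, were no later than 01 May 2024, so new wording cannot change conduct.

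Much of this stands. A reader might infer that two sites could handle the same event in opposite ways and both comply. The documents do not support that: a site that continues dosing departs from the later sentence of 7.2.2, and nothing in 10.1 authorises it to do so. What survives is narrower. The sensible reading has to be constructed, because the first paragraph has no allergic exception and the list described as full lacks the criterion. A site working from that paragraph and that list could continue without noticing the departure. The end of dosing limits what an amendment can achieve, but does not remove the need to explain what the discontinuation count represents.

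**Conclusion.** The point holds as a protocol inconsistency. For a non-severe allergic reaction, the two paragraphs of 7.2.2 and the list in 10.1 do not give the same instruction, and the difference reaches participant safety and one component of the core primary endpoint. The size is undetermined: no numeric effect is claimed beyond the per-participant figure above. The conclusion assumes only that non-severe allergic reactions can occur and that some sites may have worked from the first paragraph of 7.2.2 and from 10.1. Overall adverse event incidence is not affected.

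A reader might also infer that the SAP's handling of hypersensitivity compounds the problem. SAP Section 5.7.4 says "Hypersensitivity events will be identified using the SMQ of hypersensitivity (narrow and broad scope), SMQ of angioedema (narrow and broad scope", adds the anaphylactic reaction query, and sets no window around infusions. That is a separate matter. The discontinuation table counts events that led to stopping and takes nothing from these queries, so a window would leave it unchanged. Nor is the missing window an oversight: SAP Table 11 openly drops the analysis of events within 2 hours of infusion, citing early termination, the abbreviated report and analyses judged uninformative. SAP Table 6 still plans related and serious hypersensitivity tables, and the listings hold event onset dates and infusion records. Any estimate of how far background events would hide infusion reactions needs a background rate that the documents do not give, and it would not measure the protocol conflict.

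**What to change.** Reconcile the first paragraph of 7.2.2, its later paragraph and the list in 10.1 so that all three give the same instruction for a non-severe allergic reaction. Which instruction is for the sponsor to decide. If 10.1 is to remain the full list, it must carry whatever allergic criterion is kept.

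Because dosing has ended, also state in the study report, beside the tables of adverse events that led to discontinuation, that the protocol held conflicting rules for these reactions. The planned adverse event listing already carries preferred term, severity and action on study treatment, so non-severe allergic events and what was done after each can be identified there.

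The cost is a few lines of protocol wording and a short note in the report, with no new data and no new analysis. Splitting the hypersensitivity tables by time from infusion is optional and is not part of this correction.
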